5.3 Exclusion criteria

Patients eligible for this study must not meet **any** of the following criteria:

1. Hypersensitivity to everolimus, to other rapamycin derivatives, or to any of the excipients.
2. Inability to attend scheduled clinic visits or scheduled tests.
3. Patient who is unwilling to receive Afinitor treatment due to any reason.
4. Pregnant or nursing (lactating) women, where pregnancy is defined as the state of a female after conception and until the termination of gestation, confirmed by a positive hCG laboratory test.

Women of child-bearing potential, who are or might become sexually active, must be informed of the need to prevent pregnancy during the study. Women of child-bearing potential, defined as all women physiologically capable of becoming pregnant (including female pediatric patients who are menarcheal or who become menarcheal during the study), must use highly effective contraception during study treatment and for 8 weeks after stopping treatment. Highly effective contraception methods include:

- Total abstinence (when this is in line with the preferred and usual lifestyle of the subject. Periodic abstinence (e.g., calendar, ovulation, symptothermal, post-ovulation methods) and withdrawal are not acceptable methods of contraception
- Female sterilization (have had surgical bilateral oophorectomy with or without hysterectomy) or tubal ligation at least six weeks before taking study treatment. In case of oophorectomy alone, only when the reproductive status of the woman has been confirmed by follow up hormone level assessment
- Male sterilization (at least 6 months prior to screening). The vasectomized male partner should be the sole partner for that subject with the appropriate post-vasectomy documentation of the absence of sperm in the ejaculate)
- Barrier methods of contraception: Condom or Occlusive cap (diaphragm or cervical/vault caps) with spermicidal foam/gel/film/cream/ vaginal suppository
- Use of oral, injected or implanted hormonal methods of contraception or placement of an intrauterine device (IUD) or intrauterine system (IUS), or other forms of hormonal contraception that have comparable efficacy (failure rate <1%), for example hormone vaginal ring or transdermal hormone contraception

In case of use of oral contraception women should have been stable on the same pill for a minimum of 3 months before taking study treatment.

5. Prior therapy with mTOR inhibitors (e.g. sirolimus, temsirolimus, everolimus).
6. Use of an investigational drug within the 30 days prior to enrollment.
7. Any severe and/or uncontrolled medical conditions which could cause unacceptable safety risks or compromise compliance with the protocol, such as: Impairment of gastrointestinal function or gastrointestinal disease that may significantly alter the absorption of study drug (e.g., ulcerative disease, uncontrolled nausea, vomiting, diarrhea, etc).
8. Known history of seropositivity for human immunodeficiency virus (HIV)
9. Any cause that the investigator considers will harm the patient's benefit if participate in this study and please specify.

6 Treatment

6.1 Study treatment

This is a single arm, open-label study, and the investigational drug used in the course of this trial is Afinitor® (everolimus, 2.5 mg tablet, 5 mg tablet).

6.1.1 Dosing regimen

Everolimus will be dosed starting on Treatment Day 1 (Visit 1). Patients will be instructed to take Everolimus at a starting dose of 10 mg orally once daily. Everolimus should be administered orally once daily at the same time every day, either consistently with or consistently without food and be swallowed whole with a glass of water and should not be chewed or crushed. A change of dose might be required during the treatment, please refer to [Section 6.3](#) and the Package Insert for more details.

If vomiting occurs, no attempt should be made to replace the vomited dose. Patients should be instructed that if they miss a dose on one day, they must not take any extra dose the next day, but instead to immediately contact the study center as soon as possible to ask for advice.

6.1.2 Ancillary treatments

Not applicable.

6.1.3 Rescue medication

Not applicable.

6.1.4 Treatment duration

Patient may continue treatment with the study drug until the patient experiences unacceptable toxicity, disease progression and/or treatment is discontinued at the discretion of the investigator or withdrawal of consent, if the patient is still on treatment after 2 years, he/she will be shifted to commercial drug.

6.2 Dose escalation guidelines

Not applicable.

6.3 Dose modifications

6.3.1 Dose modification and dose delay

For patients who do not tolerate the protocol-specified dosing schedule, dose adjustments are permitted in order to allow the patient to continue the study treatment.

These changes must be recorded on the Dosage Administration Record CRF.

Management of severe or intolerable adverse drug reactions (ADRs) may require temporary dose interruption (with or without dose reduction) or discontinuation of everolimus therapy. If dose reduction is required, the suggested dose is approximately 50% lower than the daily dose

previously administered. For dose reductions below the lowest available tablet strength, alternate day dosing should be considered.

If a patient has already decreased 2 dose levels, no further dose reduction is permitted. Patients who need an additional dose reduction will be required to discontinue everolimus/placebo or comparator drug.

Table 6-1 summarizes the recommendations for dose interruption, reduction, or discontinuation of everolimus in the management of ADRs. General management recommendations are also provided as applicable. Clinical judgment of the treating physician should guide the management plan of each patient based on individual benefit/risk assessment.

Table 6-1 Afinitor Dose Adjustment and Management Recommendation for Adverse Drug Reaction

Adverse Drug Reaction	Severity ^a	Everolimus Dose Adjustment ^b and Management Recommendations
	Grade 1 Asymptomatic, radiographic findings only	No dose adjustment required. Initiate appropriate monitoring.
	Grade 2 Symptomatic, not interfering with ADL ^c	Consider interruption of therapy, rule out infection and consider treatment with corticosteroids until symptoms improve to \leq grade 1. Re-initiate Everolimus at a lower dose. Discontinue treatment if failure to recover within 4 weeks.
Non-infectious pneumonitis	Grade 3 Symptomatic, interfering with ADL ^c ; O ₂ indicated	Interrupt Everolimus until symptoms resolve to \leq grade 1. Rule out infection, and consider treatment with corticosteroids. Consider re-initiating Everolimus at a lower dose. If toxicity recurs at grade 3, consider discontinuation.
	Grade 4 Life-threatening, ventilatory support indicated	Discontinue Everolimus, rule out infection, and consider treatment with corticosteroids.

Adverse Drug Reaction	Severity ^a	Everolimus Dose Adjustment ^b and Management Recommendations
Stomatitis	Grade 1	No dose adjustment required. Manage with non-alcoholic or salt water (0.9%) mouth wash several times a day.
	Grade 2	Temporary dose interruption until recovery to grade ≤ 1 . Re-initiate Everolimus at the same dose. If stomatitis recurs at grade 2, interrupt dose until recovery to grade ≤ 1 . Re-initiate Everolimus at a lower dose. Manage with topical analgesic mouth treatments (e.g. benzocaine, butyl aminobenzoate, tetracaine hydrochloride, menthol or phenol) with or without topical corticosteroids (i.e. triamcinolone oral paste). ^d
	Grade 3	Temporary dose interruption until recovery to grade ≤ 1 . Re-initiate Everolimus at a lower dose. Manage with topical analgesic mouth treatments (i.e. benzocaine, butyl aminobenzoate, tetracaine hydrochloride, menthol or phenol) with or without topical corticosteroids (i.e. triamcinolone oral paste). ^d
	Grade 4	Discontinue Everolimus and treat with appropriate medical therapy.
Other nonhematologic toxicities (excluding metabolic events)	Grade 1	If toxicity is tolerable, no dose adjustment required. Initiate appropriate medical therapy and monitor.
	Grade 2	If toxicity is tolerable, no dose adjustment required. Initiate appropriate medical therapy and monitor.
	Grade 3	If toxicity becomes intolerable, temporary dose interruption until recovery to grade ≤ 1 . Re-initiate Everolimus at the same dose. If toxicity recurs at grade 2, interrupt Everolimus until recovery to grade ≤ 1 . Re-initiate Everolimus at a lower dose. Temporary dose interruption until recovery to grade ≤ 1 . Initiate appropriate medical therapy and monitor.
	Grade 4	Consider re-initiating Everolimus at a lower dose. If toxicity recurs at grade 3, consider discontinuation. Discontinue Everolimus and treat with appropriate medical therapy.

Adverse Drug Reaction	Severity ^a	Everolimus Dose Adjustment ^b and Management Recommendations
Metabolic events (e.g. hyperglycemia, dyslipidemia)	Grade 1	No dose adjustment required. Initiate appropriate medical therapy and monitor
	Grade 2	No dose adjustment required. Manage with appropriate medical therapy and monitor
	Grade 3	Temporary dose interruption. Re-initiate Everolimus at a lower dose. Manage with appropriate medical therapy and monitor.
	Grade 4	Discontinue Everolimus and treat with appropriate medical therapy.

Physicians should always manage patients according to their medical judgment based on the particular clinical circumstances.

^a Severity grade description: 1 = mild symptoms; 2 = moderate symptoms; 3 = severe symptoms; 4 = life-threatening symptoms,

^b If dose reduction is required, the suggested dose is approximately 50% lower than the dose previously administered.

^c Activities of daily living (ADL)

^d Avoid using agents containing hydrogen peroxide, iodine, and thyme derivatives in management of stomatitis as they may worsen mouth ulcers.

Renal Impairment

No clinical studies were conducted with everolimus in patients with decreased renal function. Renal impairment is not expected to influence drug exposure and no dosage adjustment of everolimus is recommended in patients with renal impairment.

Hepatic Impairment

Hepatic impairment will increase the exposure to everolimus. Dose adjustments are recommended:

- Mild hepatic impairment (Child-Pugh class A): The recommended dose is 7.5 mg daily; the dose may be decreased to 5mg if not well tolerated.
- Moderate hepatic impairment (Child-Pugh class B): The recommended dose is 5 mg daily; the dose may be decreased to 2.5 mg if not well tolerated.
- Severe hepatic impairment (Child-Pugh class C): If the desired benefit outweighs the risk, a dose of 2.5 mg daily maybe used but must not be exceeded.

Dose adjustments should be made if a patient's hepatic (Child-Pugh) status changes during treatment.

Dose adjustments for QTcF prolongation.

1. Assess the quality of the ECG recording and the QT value and repeat if needed
2. Interrupt study treatment
3. Determine the serum electrolyte levels (in particular hypokalemia, hypomagnesemia). If abnormal, correct abnormalities before resuming study drug treatment.
4. Review concomitant medication associated with QT prolongation, including drugs with a “Known”, “Possible”, or “Conditional risk of Torsade de Pointes”, and drugs with the potential to increase the risk of study drug exposure related QT prolongation

5. Check study drug dosing schedule and treatment compliance
6. Consider collecting a time-matched PK sample, and record time and date of last study drug intake.

After confirming ECG reading at site, if QTcF > 500 msec

- Interrupt study treatment
- Repeat ECG and confirm ECG diagnosis by a cardiologist or central ECG lab
- If QTcF confirmed > 500 msec:
 - Correct electrolytes, eliminate culprit concomitant treatments, and identify and address clinical conditions that could potentially prolong the QT as per the ECG and QTc Clinical Safety Standards Guidelines Section 3.3.1.
 - Consult with a cardiologist (or qualified specialist)
 - Increase cardiac monitoring as indicated, until the QTcF returns to \leq 480 msec.
- After resolution to \leq 480 msec, consider re-introducing treatment at reduced dose, and increase ECG monitoring for the next treatment(s):
 - If QTcF remains \leq 500 msec after dose reduction, continue planned ECG monitoring during subsequent treatment

If QTcF recurs > 500 msec after dose reduction, discontinue patient from trial.

6.3.2 Follow-up for toxicities

All patients will be followed for adverse events and serious adverse events for 30 days following the last dose of study drug. Beyond these 30 days, any serious adverse events that are suspected to be related to the study drug will also be collected.

6.3.2.1 Follow up on potential drug-induced liver injury (DILI) cases

Patients with transaminase increase combined with TBIL increase may be indicative of potential DILI, and should be considered as clinically important events.

The threshold for potential DILI may depend on the patient's baseline AST/ALT and TBIL value; patients meeting any of the following criteria will require further follow-up as outlined below:

- For patients with normal ALT and AST and TBIL value at baseline: AST or ALT $>$ 3.0 x ULN combined with TBIL $>$ 2.0 x ULN
- For patients with elevated AST or ALT or TBIL value at baseline: [AST or ALT $>$ 2 x baseline AND $>$ 3.0 x ULN] OR [AST or ALT $>$ 8.0 x ULN], combined with [TBIL $>$ 2 x baseline AND $>$ 2.0 x ULN]

Medical review needs to ensure that liver test elevations are not caused by cholestasis, defined as ALP elevation $>$ 2.0 x ULN with R value $<$ 2 in patients without bone metastasis, or elevation of ALP liver fraction in patients with bone metastasis.

Note: (The R value is calculated by dividing the ALT by the ALP, using multiples of the ULN for both values. It denotes whether the relative pattern of ALT and/or ALP elevation is due to cholestatic (R \leq 2), hepatocellular (R \geq 5), or mixed (R $>$ 2 and $<$ 5) liver injury).

In the absence of cholestasis, these patients should be immediately discontinued from study drug treatment, and repeat LFT testing as soon as possible, preferably within 48 hours from the awareness of the abnormal results. The evaluation should include laboratory tests, detailed history, physical assessment and the possibility of liver metastasis or new liver lesions, obstructions/compressions, etc.

1. Laboratory tests should include ALT, AST, albumin, creatine kinase, total bilirubin, direct and indirect bilirubin, GGT, prothrombin time (PT)/INR and alkaline phosphatase.
2. A detailed history, including relevant information, such as review of ethanol, concomitant medications, herbal remedies, supplement consumption, history of any pre-existing liver conditions or risk factors, should be collected.
3. Further testing for acute hepatitis A, B, C or E infection and liver imaging (e.g. biliary tract) may be warranted.
4. Obtain PK sample, as close as possible to last dose of study drug, if PK analysis is performed in the study.
5. Additional testing for other hepatotropic viral infection (CMV, EBV or HSV), autoimmune hepatitis or liver biopsy may be considered as clinically indicated or after consultation with specialist/hepatologist.

All cases confirmed on repeat testing meeting the laboratory criteria defined above, with no other alternative cause for LFT abnormalities identified should be considered as “medically significant”, thus, met the definition of SAE ([Section 8.2.1](#)) and reported as SAE using the term “potential drug-induced liver injury”. All events should be followed up with the outcome clearly documented

6.4 Concomitant medications

In clinical trials and post-marketing spontaneous reports, angioedema has been reported with and without concomitant use of angiotensin-converting-enzyme (ACE) inhibitors. The risk of angioedema events may be increased with concomitant administration of ACE inhibitors. Patients must be instructed not to take any additional medications (over-the-counter, herbal or other products) during the study without prior consultation with the investigator. All medications taken within 30 days of starting study treatment and during the study until the last dose should be reported on the Concomitant Medication/Significant Non-drug Therapy CRF. Co-administration with strong CYP3A4 inhibitors, strong CYP3A4 inducers, St. John’s Wort (*Hypericum perforatum*), and grapefruit, grapefruit juice, and other foods that are known to inhibit cytochrome P450 and PgP activity should be avoided during the treatment (refer to Package Insert for more details). Contraindications include hypersensitivity to the active substance, to other rapamycin derivatives, or to any of the excipients.

For concomitant medications deemed necessary for the care of the patient, dose modifications may be required and please refer to [Section 6.3](#) and Package Insert for detailed instructions. The concomitant medications should be documented in CRF.

6.4.1 Permitted concomitant therapy

The patient must be told to notify the investigational site about any new medications he/she takes after the start of the study drug. All medications (other than study drug) and significant non-drug therapies (including physical therapy, herbal/natural medications and blood transfusions) administered during the study must be listed on the Concomitant Medications or the Procedures and Significant Non-Drug Therapies CRF.

6.4.2 Permitted concomitant therapy requiring caution and/or action

Cytochrome P450 and P-glycoprotein (PgP) inhibitors/inducers/substrates

Everolimus is metabolized by CYP3A4 in the liver and to some extent in the intestinal wall.

Therefore, the following are recommended:

Co-administration with strong inhibitors of CYP3A4/PgP should be avoided and may cause increased everolimus concentrations. Co-administration with moderate CYP3A4/PgP inhibitors should be used with caution. If a patient requires co-administration of moderate CYP3A4/PgP inhibitors, reduce the dose of study drug to half the currently used dose. Additional dose reductions may be required to manage toxicities. If the inhibitor is discontinued, consider a washout period of at least 2-3 days (average for the most commonly used moderate inhibitors), before the study drug dose is returned to the dose used prior to initiation of the moderate CYP3A4/PgP inhibitor.

If a patient requires co-administration of strong CYP3A4 inducer, an increase in the dose of study drug up to twice the currently used daily dose should be considered, using 5 mg increments or less. This dose adjustment of study drug is predicted to achieve similar AUC to the range observed without inducers. However, there are no clinical data with this dose adjustment in patients receiving strong CYP3A4 inducers. If the strong inducer is discontinued, consider a washout period of at least 3-5 days (reasonable time for significant enzyme de-induction), before the study drug dose is returned to the dose used prior to initiation of the strong CYP3A4/PgP inducer.

Please refer to [Table 6-2](#) listing relevant inducers and inhibitors of CYP3A and to [Table 6-3](#) for a list of relevant substrates, inducers, and inhibitors of PgP.

Table 6-2 Clinically relevant drug interactions: inducers, and inhibitors of isoenzyme CYP3A

Inducers

Strong inducers:

avasimibe, carbamazepine, phenytoin, rifampin, St. John's wort, rifabutin, phenobarbital, mitotane, enzalutamide

Moderate inducers:

bosentan, efavirenz, etravirine, modafinil, naftillin, genistein, ritonavir, thioridazine, tipranavir, semagacestat, talvirilane, lopinavir, lersivirine,

Weak inducers:

amprenavir, aprepitant, armodafinil bexarotene, clobazam, danshe, dexamethasone, echinacea, garlic , gingko (ginkgo biloba), glycyrrhizin, methylprednisolone, nevirapine, oxcarbazepine, pioglitazone, prednisone, pleconaril, primidone, raltegravir, rufinamide, sorafenib, telaprevir, terbinafine, topiramate, troglitazone, vinblastine, eslicarbazepine, ginseng, vemurafenib, boceprevir, sulfapyrazone, ticagleror, virciviroc/ritonavir, ritonavir, ticlopidine, brivacetam, Stribild (combo of elvitegravir, cobicistat, emtricitabine, and tenofovir), quercetin.

Inhibitors

Strong inhibitors:

boceprevir, clarithromycin, conivaptan, grapefruit juice, indinavir, itraconazole, ketoconazole, lopinavir/ritonavir, mibefradil, nefazodone, neflifinavir, posaconazole, ritonavir, saquinavir, sequinavir/ritonavir, telaprevir, telithromycin, voriconazole, indinavir/ritonavir, tipranavir/ritonavir, cobicistat, troleandomycin, danoprevir/ritonavir, eltegravir/ritonavir,

Moderate inhibitors:

amprenavir, aprepitant, atazanavir, ciprofloxacin, darunavir/ritonavir, diltiazem, erythromycin, fluconazole, fosamprenavir, grapefruit juice, nilotinib imatinib, tofisopam, cyclosporin, ciprofloxacin, verapamil, dronedarone, crizotinib, casopitant, amprenavir, atazanavir/ritonavir, duranavir, netupitant, schisandra sphenanthera , cimetidine, lomitapide

Weak inhibitors:

tabimorelin, ranolaxine, fosapreptitant, Seville orange, amlodipine, clozoxazone, fluvoxamine, ranitidine, goldenseal ,clotrimazole, tacrolimus, cilostazol, ticagrelor, ivacaftor, roxithromycin, propiverine, isoniazid, berberine, oral contraceptives, peppermint oil, delavirdine, simeprevir, atorvastatin, tolvaptan, almorexant, linagliptin, resveratrol, lacipidine, cranberry juice, nilotinib, pazopanib, evolimus, blueberry juice, alprazolam, bicalutamide, sitaxentan, azithromycin, ginkgo, teriflunomide, alprazolam, amiodarone, amlodipine, bicalutamide, cilostazol, cimetidine, cyclosporine, fluoxetine, isoniazid, ranitidine, ranolazine, tipranavir/ritonavir, zileuton

Table 6-3 Clinically relevant drug interactions: substrates, inducers, inhibitors of PgP and PgP/CYP3A dual inhibitors

Substrates

digoxin, quinidine, paclitaxel, cyclosporine, sirolimus, tacrolimus, fentanyl, phenytoin, aliskiren, ambrisentan, atorvastatin, atorvastatin acid, azithromycin, cerivastatin, colchicine, CP-481,715, cyclosporine, dabigatran, digoxin, docetaxel, domperidone, doxorubicin, fentanyl, fexofenadine, lapatinib, linezolid, loperamide, maraviroc, nevirapine, paclitaxel, proguanil, quinidine, ranolazine, ritonavir, saquinavir, simvastatin, sirolimus, sofosbuvir, tacrolimus, ticagrelor, voclosporin, afatinib, alfuzosin, aliskiren, alogliptin, ambrisentan, apixaban, apremilast, aprepitant, boceprevir, bosentan, carvedilol, carvedilol, caspofungin, ceritinib, citalopram, colchicine, cyclosporine, dabigatran, digoxin, doxepin, doxorubicin, eribulin, everolimus, fidaxomicin, fluvastatin, fosamprenavir, gatifloxacin, idelalisib, iloperidone, indacaterol, irbesartan, lacosamide, lapatinib, levetiracetam, levofloxacin, linagliptin, losartan, maraviroc, mirabegron, moxifloxacin, naloxegol, nateglinide, nintedanib, olodaterol, pantoprazole, paroxetine, pazopanib, posaconazole, pravastatin, quinine, ranolazine, riociguat, risperidone, rivaroxaban, saquinavir, silodosin, simeprevir, sirolimus, sitagliptin, sorafenib, telaprevir, tenofovir, ticagrelor, tipranavir, tolvaptan, topotecan, umeclidinium, valsartan, vardenafil, vincristine, voriconazole

Inducers

avasimibe, carbamazepine, efavirenz, genistein, phenytoin, quercetin, rifampin, St. John's wort extract

PgP Inhibitors and PgP/CYP3A Dual Inhibitors

PgP Inhibitors

alogliptin, canagliflozin, cremophor RH40, curcumin, ketoconazole, lapatinib, lopinavir/ritonavir, mirabegron, propafenone, simeprevir, valspar, vandetanib, voclosporin

PgP/CYP3A Dual Inhibitors

amiodarone, azithromycin, captopril, carvedilol, clarithromycin, conivaptan, diltiazem, dronedarone, elacridar, erythromycin, felodipine, fluvoxamine, ginkgo, indinavir, indinavir/ritonavir, itraconazole, mibepradil, milk thistle, nelfinavir, nifedipine, nitredipine, paroxetine, quercetin, quinidine, ranolazine, rifampin, ritonavir, sequinavir/ritonavir, schisandra chinesis extract, St. John's wort extract, talinolol, telaprevir, telmisartan, ticagrelor, tipranavir/ritonavir, tolvaptan, verapamil

Reference: Internal Clinical Pharmacology Drug-drug interaction (DDI) memo, updated April-2015 which summarizes DDI data from three sources including the FDA's "Guidance for Industry, Drug Interaction Studies", the University of Washington's Drug Interaction Database, and Indiana University School of Medicine's Drug Interaction Table.

Vaccinations

Immunosuppressants may affect the response to vaccination and vaccination during treatment with everolimus may therefore be less effective. The use of live vaccines should be avoided during treatment with everolimus. Examples of live vaccines are: intranasal influenza, measles, mumps, rubella, oral polio, BCG, yellow fever, varicella, and TY21a typhoid vaccines.

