2.3 Rationale for dose and regimen selection

Starting dose and dose adjustment will follow the approved Chinese Package Insert. The starting dose is 10 mg once daily. The subsequent dose levels are subject to change due to severe or intolerable adverse reactions, change of liver function, changes in concomitant drug use (refer to [Section 6.3.1](#)).

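### Protocol Table 6-2 lists cimetidine and cyclosporin(e) as both moderate and weak CYP3A inhibitors, while the advice to halve everolimus attaches only to the moderate class

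*Protocol*

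**What the plan says.** Protocol Section 6.4.2 sets out recommendations by inhibitor strength. Strong CYP3A4/PgP inhibitors are to be avoided. Moderate ones are to be used with caution, and if one is required the site should "reduce the dose of study drug to half the currently used dose". Weak inhibitors are not mentioned. The section then refers sites to Table 6-2 for CYP3A inducers and inhibitors and to Table 6-3 for PgP.

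The moderate list in Table 6-2 contains the runs "tofisopam, cyclosporin, ciprofloxacin, verapamil, dronedarone" and "cimetidine, lomitapide". The weak list in the same table contains "cilostazol, cimetidine, cyclosporine, fluoxetine".

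Two other provisions bear on the point. Section 2.3 names the authority for dosing: "Starting dose and dose adjustment will follow the approved Chinese Package Insert". Section 6.4 says that patients may not take additional medicines "without prior consultation with the investigator", and for necessary concomitant medicines it refers sites to Section 6.3 "and Package Insert for detailed instructions".

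**The concern.** The strength class is what decides whether a written dose recommendation applies, and Table 6-2 is the only place in the protocol that grades inhibitors by strength. For these two drugs it gives two answers. A site that finds the moderate entry halves the dose; a site that finds only the weak entry sees nothing to do. Two sites could therefore dose the same co-medicated patient differently, each following the table as it reads it. What is at stake is patient safety and consistent dosing between sites, in a trial whose primary objective is safety.

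**Working it through.** The plan gives no figure to reproduce here. The check is a comparison of lists, a search for a tie-break, and a small dose calculation.

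**1. Overlap of the inhibitor lists in Table 6-2.** Three reading conventions were used: cyclosporin and cyclosporine are one drug, ranolaxine is ranolazine, and the moderate entry for nilotinib and imatinib, printed without a comma, is split in two.

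| Class | Entries | Distinct |
|---|---|---|
| Strong | 24 | 24 |
| Moderate | 26 | 24 |
| Weak | 52 | 45 |

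The moderate list repeats two of its own entries (26 − 2 = 24) and the weak list repeats seven (52 − 7 = 45). The overlaps between classes are:

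- Moderate and weak: cimetidine, cyclosporin(e), nilotinib.
- Strong and moderate: grapefruit juice.
- Strong and weak: tipranavir/ritonavir.

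Nilotinib is set aside for the main point, because Section 6.4.3 does not permit other systemic anticancer agents before documented progression. Two drugs remain.

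**2. Does anything in the protocol break the tie?**

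- Table 6-2 has no footnote on precedence.
- Section 2.3 names changes in concomitant medication as a reason to change dose and points to Section 6.3.1, but Section 6.3 contains no CYP3A rule.
- Table 6-3 has cyclosporine only among the PgP substrates ("digoxin, quinidine, paclitaxel, cyclosporine, sirolimus, tacrolimus"). It does not list cimetidine, has neither drug among the PgP or dual inhibitors, and does not grade inhibitors by strength.
- The exclusion criteria in Section 5.3 remove neither drug.

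So the protocol text does not settle the class of either drug.

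**3. Dose consequence of a missed halving.** Recommended dose under the moderate rule = 0.5 × current dose.

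- Starting dose (Section 6.1.1), 10 mg/day: 0.5 × 10 = 5 mg/day. If the halving is missed, 10 mg/day is taken; 10 / 5 = 2.0.
- Current dose 5 mg/day, for example Child-Pugh B (Section 6.3.1): 0.5 × 5 = 2.5 mg/day. If the halving is missed, 5 mg/day is taken; 5 / 2.5 = 2.0.

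These ratios hold only if moderate is the correct class. If weak is correct, Section 6.4.2 calls for no reduction, the full dose is the intended one, and the excess is zero.

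**The case against.** The strongest reply is that there are no competing rules. Section 6.4.2 has one explicit recommendation, triggered by a moderate inhibitor. Both drugs are on the moderate list, which comes before the weak one, and the weak list carries no instruction that could cancel the trigger. This stands. A reader might infer that the protocol gives two contradictory dose instructions; it does not. That a weak inhibitor needs no change is only an inference from silence. What remains is the risk that a site looks up only the weak entry.

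Second, the protocol makes the Package Insert the authority for dose adjustment, and it may classify both drugs. That also stands, and it limits how much can be said about the practical risk. It does not make the table consistent, and sites are told to use the table.

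Third, the halving recommendation is worded for CYP3A4/PgP inhibitors while Table 6-2 covers CYP3A only, so it could be read more narrowly. But Section 6.4.2 itself links the recommendation to Table 6-2, and no other list grades strength.

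Fourth, controls exist: patients must consult the investigator before taking new medicines (Section 6.4) and notify the site of any they take (Section 6.4.1). This lowers the risk, but does not tell the investigator which entry to follow.

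Fifth, a default to halving has a cost at a current dose of 2.5 mg/day, where the result falls below the lowest tablet strength and Section 6.3.1 would have alternate-day dosing considered. That cost arises for every moderate inhibitor under the existing recommendation; it is not created by correcting the table.

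**Conclusion.** The double listing is certain on the face of the current protocol. It is an internal inconsistency in an operational dosing table, not a design choice. A likely origin is the merging of source lists: the note under Table 6-3 says the reference memo summarizes three sources, and the weak list ends in a second alphabetical run that repeats earlier entries. That is an inference, and nothing rests on it.

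The size is small. Two drugs are involved. A missed halving doubles the dose during co-medication if moderate is the correct class and adds nothing if weak is correct; the documents available here do not say which. The number of patients affected is unknown and probably few or none.

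A reader might infer that patients were overdosed, or that adverse-event incidence is distorted. The documents support neither: they do not show that any patient took either drug, and no planned analysis depends on the classification.

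**What to change.** List cimetidine and cyclosporin(e) in one class each in Table 6-2, confirmed by the sponsor's clinical pharmacology group against the Package Insert. Until that is done, state that the moderate-inhibitor recommendation (halve the current dose) applies to both. The downside of this interim rule is possible under-dosing during co-medication if weak proves to be the correct class. In the same edit, reconcile the other cross-class repeats, for example grapefruit juice, tipranavir/ritonavir and nilotinib.

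The cost is a table edit and one sentence in a protocol amendment or investigator letter, with no added data collection. The change cannot alter doses already taken. Concomitant medications are already entered in the database (Protocol Table 7-1) and are coded and listed (SAP Section 5.3.5), so the sponsor can check from existing data whether any patient took either drug.
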